# 2.3.3. Benefit-Risk Assessment for Study Participation

The risk/benefit of JNJ-40411813 is favorable and the currently available safety and efficacy data support the proposed clinical trial 40411813EPY2001 to investigate efficacy and safety of JNJ-40411813 in participants with focal onset epilepsy.

More detailed information about the known and expected benefits and risks of JNJ-40411813 may be found in the current IB for JNJ-40411813.

# 3. OBJECTIVES AND ENDPOINTS a

Objectives	Endpoints
Primary	
The primary objective of this study is to evaluate the efficacy of up to 3 dose levels of adjunctive JNJ-40411813 compared to placebo based on the time to baseline monthly seizure count in participants with focal onset seizures who are receiving levetiracetam or brivaracetam and up to 3 other AEDs	Time to baseline monthly seizure count is defined, for each patient, as the number of days until the patient experienced the number of seizures equal to baseline monthly seizure count, up to the end of the 12-week doubleblind treatment period.
Secondary  To evaluate the overall safety and tolerability of adjunctive JNJ-40411813 compared to placebo in participants with focal onset seizures who are receiving levetiracetam or brivaracetam and up to 3 other AEDs.	Adverse events, significant changes in vital signs, ECG and safety laboratory results.
To evaluate the efficacy of up to 3 dose levels of adjunctive JNJ-40411813 compared to placebo based on percent reduction in the double-blind monthly seizure count, relative to the pre-randomization monthly seizure count, in participants with focal onset seizures.	Percent reduction in the double-blind monthly seizure count is defined as the double-blind monthly seizure count minus the baseline monthly seizure count, divided by the baseline monthly seizure count. The double-blind monthly seizure count is defined as the total number of observable focal onset seizures occurring during the 12-week double blind treatment period, multiplied by 28/X DB , where is the number of days comprising the double-blind period.
	Observable seizures that will be counted during baseline and throughout the study

<sup>a This section has been amended by Amendment INT-1 and INT-3

\_

Objectives	Endpoints
	include focal aware seizures with motor signs,
	focal impaired awareness seizures and focal
	to bilateral tonic-clonic seizures. Focal aware
	seizures without motor signs, myoclonic, or
	other generalized seizures will not be counted.
To evaluate the efficacy of JNJ-40411813	The proportion of participants with no
over the double-blind period using percent	seizures during the double-blind period, and
participants with seizure freedom and percent	the proportion with a greater than 50%
responders (>50% seizure rate reduction).	reduction in monthly seizure count relative to
	baseline monthly seizure count.
To evaluate the pharmacokinetics (PK) of	Plasma concentrations of JNJ-40411813 and
JNJ-40411813 and selected metabolites and	levetiracetam or brivaracetam at baseline
levetiracetam or brivaracetam in participants	(Day 1) and on study weeks 4, 8, and 12
with focal onset seizures who are receiving	
levetiracetam or brivaracetam and up to 3	
other AEDs.	
Exploratory	

# Hypothesis

The hypothesis of this study is that JNJ-40411813 added to treatment that includes levetiracetam or brivaracetam significantly prolongs the time to baseline monthly seizure count compared to placebo add-on treatment.

CONFIDENTIAL - FOIA Exemptions Apply in U.S.

# 4. STUDY DESIGN

# 4.1. Overall Designa

This study as per Amendment INT-2 will consist of a double-blind treatment period and an openlabel extension (OLE) period. Details about the OLE period are described in Section 10.

This is a double-blind, randomized, parallel, placebo-controlled study with the option for an OLE period. The study will consist of 1 to a maximum of 3 cohorts. In each cohort, for each participant the study consists of a screening visit, an 8-week prospective pretreatment baseline period, an up to 12-week double-blind treatment period and, for those participants electing not to enter the OLE period, a follow-up telephone visit 2 weeks after the last dose of study intervention. Participants have the option to enter an OLE period, in which treatment with JNJ-40411813 may be continued until the product becomes available by prescription, or until development of JNJ-40411813 in this indication ceases. The total maximal duration of the study is approximately 22 weeks for each participant, up to the time of entry into the OLE period.

Participants from 18 to 69 years (inclusive) old with an established diagnosis of focal onset seizures will be enrolled in the study. For the first cohort, approximately 80 eligible participants will be initially enrolled to ensure that approximately 60 participants are randomly assigned in a 2:1 ratio to receive either JNJ-40411813 [CIIIII] placebo. For each following cohort, approximately 60 eligible participants will be initially enrolled to ensure that approximately 50 participants are randomly assigned in a 4:1 ratio to receive either JNJ-40411813 [CIIIII] placebo.

In each cohort, participants will be CCI	CCI

At least 20% of the participants must be included in each of the two groups.

After giving written informed consent, participants will be screened immediately prior to the start of the pretreatment baseline period to ascertain their eligibility for the study per the inclusion and exclusion criteria. Upon completion of all informed consent form (ICF) procedures, recording of Aes and concomitant medication will start.

After the screening visit, the data of the participant may be subject to an adjudication process by independent experts from the epilepsy consortium. In this adjudication process the experts may decide whether the participant meets eligibility criteria to participate in the study.

After screening, if they meet the in- and exclusion criteria for which data are available, participants can start the 8-week prospective pretreatment baseline period pending the results of the central laboratory and – if applicable – the adjudication process. However, when the results of these

-

[figure not shown]
<sup>a This section has been amended by Amendment INT-1 and INT-2 and INT-3

assessments indicate that the participant does not meet the in- and exclusion criteria, the participant will terminate the baseline period and will not be randomized to treatment.

During the 8-week prospective pretreatment baseline period participants will continue to take their prescribed AEDs (one of which must include levetiracetam or brivaracetam) without change in dosage(s); new concomitant AEDs should not be added. During the baseline period, participants will record seizure information (type and frequency of seizures) in an e-diary. Baseline monthly seizure count will be defined as the number of observable focal onset seizures recorded during the baseline period, multiplied by  $28/X_{\rm BL}$ , where  $X_{\rm BL}$  is the number of days comprising the baseline.

Participants must be compliant with the recording of information in the subject e-diary throughout the study. Observable seizures that will be counted during baseline and throughout the study, include focal aware seizures with motor signs, focal impaired awareness seizures and focal to bilateral tonic-clonic seizures. Focal aware seizures without motor signs, myoclonic, or other generalized seizures will not be counted.

Participants who meet study entry criteria at the end of the prospective pretreatment baseline period will be randomized to JNJ-40411813 or placebo, CCI . The dosage(s) of concomitant AEDs should not be increased, and new concomitant AEDs should not be added to the treatment regimen.

Participants are encouraged to complete at least the first 4 weeks of treatment when there are no safety concerns. Participants who have exceeded their pre-randomization monthly seizure count at Week 4, or within any 4-week interval after Week 4 ("4-week sliding window approach") up to Week 12, will have the option to discontinue the study drug for lack of efficacy and to perform the end of study/early withdrawal visit, to continue double blind treatment, or to enter the OLE period. Participants who have not exceeded the pre-randomization seizure count will continue the double-blind treatment period through Week 12 and will have the option to perform the end of study visit or to enter the OLE period.

Procedures performed in the OLE period are described in Section 10.

Participants will visit the study center according to the schedule in the Schedule of Activities (SoA).

After at least 55 patients in Cohort 1 and after at least 45 patients in Cohort 2 have completed at least 4 weeks of treatment, an interim unblinded review of all cumulative safety, PK and efficacy data of JNJ-40411813 available to that date will be performed to decide on whether there should be any addition or modification to the dose(s) in the following cohorts and subsequent clinical studies. If the results of the review are inconclusive with respect to the assessment of efficacy, a second interim review of the same cohort may be done after the last participant has completed the 12-week visit.

See Figure 1 for the study flow diagram.

The study assessments will be completed as described in the SoA in Section 1.2.

# Follow-up examination or early withdrawal

All participants will have a follow-up visit by telephone (Visit 8) at 2 weeks  $\pm 2$  days after the last dose of study intervention. Participants who prematurely withdraw from the study should complete Visit 7. Participants who continued treatment to the end of the double-blind treatment period (Week 12) or have completed the study as per Section 7.2 will continue to collect information on the number of seizures they experience using the e-diary until 2 weeks after the last dose of study medication. The procedures to be completed during this visit are listed in the SoA.

# 4.2. Scientific Rationale for Study Design

# Design aspects and placebo control

A 1 to 3-cohort approach has been chosen to limit the number of participants exposed to study intervention and study procedures. Starting in Cohort 1 with a dose that is well tolerated but also expected to generate clinical effect, a rational decision may be taken based on ongoing assessment of the tolerability and safety whether in successive cohorts a higher or lower dose is needed for

optimal treatment. This decision may be based on the incidence of serious adverse events, or adverse events leading to discontinuation, as a cohort approaches full enrollment. Given a low incidence of these events, decision to evaluate of a higher dosage in the following cohort can be made, without pausing screening and enrollment.

The placebo response in studies in epilepsy may be significant (Goldenholz 2016). A placebo control will be used to establish the change in seizure count and the change in safety endpoints that may occur in the absence of active treatment.

# Stratification JNJ-40411813 is metabolized mainly by CYP3A4. CCI

# **Optional dosage reduction**

As noted in the Investigator's brochure, dizziness, vertigo, coordination abnormal and fatigue are adverse drug reactions attributable to JNJ-40411813. Somnolence has also been reported. These are adverse events commonly seen with other AEDs; their frequency and severity may be related to dose and may be mitigated by temporary dose reduction or dose titration. Accordingly, if these adverse events occur with increasing frequency when dosages exceed ccl e.g. Cohort 2 and beyond, the investigator will have the option to reduce dosage temporarily, followed by rechallenge. The PI is encouraged to rechallenge the initial dose within 2 weeks if the Aes are resolved on the lower dose. If rechallenge is unsuccessful, i.e., the AEs recurred when the dose was increased, the dose may be reduced again and kept at that level.

This option will minimize the likelihood of dropout because of adverse events, and will provide experience to guide dosing instructions in future studies

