5.6.1. Extent of Exposure

The number and percentage of participants who receive study intervention will be summarized.

Descriptive statistics for duration of study intervention (N, mean, SD, median, range, minimum, maximum) will be summarized.

Duration of intervention during the double-blind phase will be summarized in the following duration categories: <2 week, 2-<4 weeks, 4-<6 weeks...10-<12 weeks for each study agent within a study intervention and presented graphically in a histogram. Cumulative duration of intervention [>=2 week, >=4 weeks, ...] will also be summarized. Frequency distribution of duration of intervention during the open-label phase (week 1-4, week 5-8,...,week 101-104, or >week 104) will also be summarized.

Total duration of intervention for the double-blind phase and open-label phase is defined as (date of last dose of study intervention – date of first dose of study intervention) +1. If the date of last dose of study intervention is missing, it will be imputed as the day prior to the double-blind or

open-label disposition date for calculating exposure duration. Descriptive statistics (N, mean, SD, median, range, minimum, maximum) of total duration of intervention will be summarized for each study drug within a study intervention.

Total dose days of intervention is defined as the total number of days that study intervention was administered to the participant (excluding days off study intervention). Descriptive statistics (N, mean, SD, median, range, minimum, maximum) of total dose days of intervention will be summarized for the double-blind phase and open-label phase for each study agent within a study intervention.

A listing to show all dose adjustments for each participant including the reason for dose adjustment will be provided.

Study intervention compliance during DB and OLE will be summarized descriptively. See Appendix 7 for further details.

The analysis will be performed on SAF and SAFOLE analysis sets.

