5.6.2. Adverse Events

The verbatim terms used in the CRF by investigators to identify adverse events will be coded using the Medical Dictionary for Regulatory Activities (MedDRA). Any AE occurring at or after the initial administration of study intervention through the day of last dose plus 5 days is considered to be treatment emergent. If the event occurs on the day of the initial administration of study intervention, and either event time or time of administration are missing, then the event will be assumed to be treatment emergent. If the event date is recorded as partial or completely missing, then the event will be considered to be treatment emergent unless it is known to be prior to the first administration of study intervention based on partial onset date or resolution date. All reported treatment-emergent adverse events will be included in the analysis. For each adverse event, the number and percentage of participants who experience at least 1 occurrence of the given event will be summarized by intervention group.

Assignment of adverse events to double-blind or open-label analysis phase, or the follow-up phase will be made based on the following rules:

Double-blind analysis phase:

All AEs that are assigned to the double-blind analysis phase as detailed below will be considered as treatment-emergent.

• For participants who did not continue to open-label treatment phase: double-blind phase start date ≤ AE onset date ≤ date of the last dose of study intervention in the double-blind phase plus 5 days.

- For participants who continued to open-label treatment phase: double-blind phase start date ≤ AE onset date ≤ earlier of (date of the last dose of study intervention in the double-blind phase + 5, open-label study intervention start date)
 - AEs that occur more than 5 days after the last dose of double-blind study intervention but prior to open-label dosing will not be considered as treatmentemergent for either the double-blind or the open-label phase. These AEs will be flagged as 'Pre-open label';

Open-label analysis phase:

All AEs that are assigned to the open-label analysis phase as detailed below will be considered as treatment-emergent.

- For participants who entered open-label treatment phase < 6 days from the last dose doubleblind study intervention: open-label phase start date < AE onset date ≤ date of the last dose of study intervention in the open-label phase plus 5 days.

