- For participants who entered open-label treatment phase ≥ 6 days from last dose of double-blind study intervention: open-label phase start date \leq AE onset date \leq date of the last dose of study intervention in the open-label phase plus 5 days.

Follow-up phase:

AEs that are assigned to the follow-up phase are not considered as treatment-emergent. AEs with onset date > date of last dose of double-blind study intervention plus 5 days will be assigned to this phase.

Summary tables will be provided for treatment-emergent adverse events:

- AEs
- Serious AEs (SAEs)
- AEs leading to discontinuation of each study drug within a study intervention/termination of study participation
- AEs by relationship to study intervention
- AEs leading to dose interruption of each study agent within a study intervention.

In addition to the summary tables, listings will be provided for participants who:

- Had SAEs
- Had AEs leading to discontinuation of study intervention/termination of study participation A listing of participants who died will be provided.

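### Dose reductions for AEs are listed but not counted by arm or cohort, so from Cohort 2 on the AE-discontinuation rate alone can understate non-severe intolerance at the assigned dose

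*Protocol*

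**What the plan says.** Protocol 4.2 (Optional dosage reduction) describes the option for dosages above a redacted level, giving Cohort 2 and beyond as the example. For dizziness, vertigo, abnormal coordination, fatigue or somnolence the investigator may lower the dose and then rechallenge. If the event returns, "the dose may be reduced again and kept at that level". Two purposes are stated: the option is to make AE dropout less likely, and it "will provide experience to guide dosing instructions in future studies".

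SAP 5.6.2 names five TEAE summary tables: all AEs, serious AEs, AEs by relationship, "AEs leading to discontinuation of each study drug within a study intervention/termination of study participation", and "AEs leading to dose interruption of each study agent within a study intervention". None covers AEs leading to dose reduction. For each AE, "the number and percentage of participants who experience at least 1 occurrence of the given event will be summarized by intervention group".

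SAP 5.6.1 has one output on dose changes: "A listing to show all dose adjustments for each participant including the reason for dose adjustment will be provided".

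Protocol 4.2 (Design aspects and placebo control) says of the choice of dose for the next cohort: "This decision may be based on the incidence of serious adverse events, or adverse events leading to discontinuation, as a cohort approaches full enrollment".

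**The concern.** The option exists to keep on treatment some participants who would otherwise stop for an AE. Where it works, those participants leave the discontinuation table, and no other AE-action table clearly picks them up.

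Two readings of the results then become hard. A low AE-discontinuation rate in Cohort 2 may mean that the dose was tolerated, or that participants stayed on by taking less. And Cohort 2 cannot be set beside Cohort 1 on this measure, because 4.2 does not describe the option for the Cohort 1 dose. The experience that 4.2 wants for later dosing (how many needed a reduction, how many returned to the assigned dose) would have to be counted by hand from a listing, with placebo participants on matching tablets counted in the same way.

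**Working it through.** There is no planned figure to reproduce, since the point is about which outputs exist. I checked the text first and then sized the effect under assumed rates.

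**Text check: could another planned output carry the information?**

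- *Interruption table (SAP 5.6.2).* The SAP does not define interruption or say that it includes reduction. Protocol 8.9, on overdose, names dose interruptions and modifications as separate things.
- *Total dose days (SAP 5.6.1).* Only days off study intervention are excluded. A day at a reduced dose counts the same as a day at the assigned dose.
- *Compliance (SAP Appendix 7).* This is tablets taken over tablets due. It does not identify who was reduced.
- *Protocol 9.4.* It asks for safety summaries by treatment and cohort, but for none on dose reduction.
- *SAP version history.* The version 2.0 entry on exposure gives summarizing the dosage adjustment form data as part of its rationale. So the data exist, but the output is a listing.

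**Illustration**

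Inputs: 40 active participants in Cohort 2 (Protocol 6.3). Assumed, because the documents give no rates: D = 2 stop for an AE (2/40 = 5%), and R = 4, 8, 12 or 16 reduce at least once for an AE (10% to 40%). Let O be the number who reduce and later stop for an AE.

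- Reduced or discontinued, each participant counted once: (R + D − O)/40
- Share of that group absent from the discontinuation table: (R − O)/(R + D − O)

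| R | O = 0: combined | O = 0: absent | O = 2: combined | O = 2: absent |
|---|---|---|---|---|
| 4 | 6/40 = 15% | 4/6 = 67% | 4/40 = 10% | 2/4 = 50% |
| 8 | 10/40 = 25% | 8/10 = 80% | 8/40 = 20% | 6/8 = 75% |
| 12 | 14/40 = 35% | 12/14 = 86% | 12/40 = 30% | 10/12 = 83% |
| 16 | 18/40 = 45% | 16/18 = 89% | 16/40 = 40% | 14/16 = 88% |

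The O = 0 columns are upper bounds for these assumed rates. They also do not measure inability to stay on the assigned dose, because a participant who is rechallenged successfully does return to it. If S reducers are rechallenged successfully and O = 0, those who stop or remain below the assigned dose number R + D − S. With S equal to half of R:

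- R = 4: (4 + 2 − 2)/40 = 4/40 = 10%
- R = 8: (8 + 2 − 4)/40 = 6/40 = 15%
- R = 12: (12 + 2 − 6)/40 = 8/40 = 20%
- R = 16: (16 + 2 − 8)/40 = 10/40 = 25%

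If every reducer is rechallenged successfully, the figure is 2/40 = 5% and the discontinuation table misses nobody in this sense.

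The same point from the other side: assume that 20%, 30% or 40% of the 40 do not tolerate the assigned dose (8, 12 or 16 participants) and that half of them reduce instead of stopping. The discontinuation table then shows 4, 6 or 8.

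**Is a test worthwhile?**

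For a combined rate of 20%, 30% or 40% on active against an assumed 5% on placebo, a one-sided 5% Fisher exact test with 40 versus 10 has power of about 5%, 35% and 66%. Counts and percentages are enough.

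**The case against.** The strongest case against is that little is hidden. All TEAEs are summarized by intervention group, and serious AEs, AEs by relationship and AEs leading to discontinuation are tabulated as well. Dizziness that led to a reduction is therefore counted and set against placebo; only the action taken is missing. Under Protocol 7.3, a severe or serious AE at least possibly related to study drug requires withdrawal, so the option cannot move those events out of the discontinuation table. Section 4.2 speaks of gaining experience and promises no placebo comparison, and dose-reduction frequency is not an endpoint. The listing, for about 50 participants, can be counted by hand. The separate analysis plans for the data review and interim review committees were not available and may hold such a table. The interim review also covers all cumulative safety data, not discontinuations alone.

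Most of this stands, and it limits the point. A reader might infer that intolerance is never compared with placebo. The documents do not support that, because TEAE incidence is compared. A reader might also infer that each reduction is a prevented dropout. No passage says so, and 4.2 encourages rechallenge.

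What does not fall is the narrower gap. TEAE incidence does not show which events led to a lower dose, and a hand count from a listing is not a planned summary. Tolerability compared with placebo is a stated secondary objective, and Protocol 4.2 names AE discontinuation as a possible basis for the next dose decision.

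**Conclusion.** The point holds as a gap in the planned summaries. Dose reductions for AEs, and the combined outcome of reducing or discontinuing for an AE, are not summarized by arm or cohort. From Cohort 2 on, the AE-discontinuation rate read alone can understate non-severe intolerance at the assigned dose, and it is not like-for-like with Cohort 1.

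The size cannot be known from the documents. The illustrative 15% to 45% against a tabulated 5%, and the 67% to 89% absent from the table, rest on assumed rates and no overlap with later discontinuation. They should not be read as estimates of how many participants cannot stay on the assigned dose; depending on rechallenge, that excess may be nil. The conclusion also assumes that reductions are not coded as interruptions, which the SAP leaves open. Neither the primary efficacy analysis nor the dose-reduction rule itself is in question here.

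**What to change.** In SAP 5.6.2, add two descriptive TEAE tables by treatment group (including placebo) and cohort: AEs leading to dose reduction, and AEs leading to dose reduction or discontinuation, with each participant counted once. State whether interruption includes reduction.

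In SAP 5.6.1, add counts by treatment group and cohort of participants with at least one reduction, rechallenged, successfully rechallenged, and below the assigned dose at the last double-blind dose. Use the dosage-adjustment data that already feed the listing. No formal test is needed.

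The cost is two or three extra tables with no new data collection. The tolerability figures may look slightly less favourable.
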